4.3. General Statistical Methods and Data Handling

4.3.1. General Methods

All output will be incorporated into Microsoft Excel or Word files, sorted and labeled according to the International Conference on Harmonisation (ICH) recommendations, and formatted to the appropriate page size(s).

Tabulations will be produced for appropriate demographic, baseline, efficacy and safety parameters. For categorical variables, summary tabulations of the number and percentage within each category (with a category for missing data) of the parameter will be presented. For continuous variables, the mean, median, standard deviation, minimum and maximum values will be presented. Time to event data will be summarized using Kaplan-Meier Methodology using 25th, 50th (median), and 75th percentiles with associated 2-sided 95% confidence intervals, as well as percent of censored observations.

Formal statistical hypothesis testing will be performed on the primary and secondary efficacy endpoints with all tests conducted at the 1-sided, 0.025 level of significance. Summary statistics will be presented, as well as confidence intervals on selected parameters, as described in the sections below.

For all analyses, baseline will be defined as the most recent measurement prior to the date and time of the administration of active treatment with Pharyngeal Electrical Stimulation or a sham treatment. Therefore, baseline may be on the same day as the start of study treatment, but prior to the administration of the study treatment.

4.3.2. Computing Environment

All descriptive statistical analyses will be performed using SAS statistical software (Version X.X), unless otherwise noted. Medical History and adverse events will be coding using MedDRA version X.X. Concomitant medications will be coded using World Health Organization (WHO) Drug version X.X.

4.3.3. Methods of Pooling Data

Not applicable to the present study.

4.3.4. Adjustments for Covariates

No formal statistical analysis that adjusts for possible covariate effects is planned.

4.3.5. Multiple Comparisons/Multiplicity

Multiplicity is not of concern for this study with a single primary efficacy endpoint.

4.3.6. Subpopulations

No analyses of subgroups of subjects are planned.

4.3.7. Withdrawals, Dropouts, Loss to Follow-up

Subjects who withdrew from the study were not to be replaced.

4.3.8. Missing, Unused, and Spurious Data

In general, there will be no substitutions made to accommodate missing data points. All data recorded on the CRF will be included in data listings that will accompany the clinical study report.

4.3.9. Visit Windows

All data will be summarized by the scheduled visits. No visit windows will be applied. If multiple assessments are collected on one visit, the last assessment will be used in the analysis.

4.4. Interim Analyses

This study follows a 3-look adaptive group sequential design with sample size re-estimation. In order to assure 180 evaluable patients with 7 day(+/- 1day) data and assuming a 20% dropout rate, approximately 225 patients will be enrolled initially.

An interim analysis for futility (non-binding) will occur after the first 60 patients complete their 7 day visit, and a second interim analysis will be performed for efficacy after 120 patients complete their 7 day visit. At the recommendation of the Data Monitoring Committee (DMC) the following actions may be taken at this second interim analysis:

- Stop the study for futility of the primary endpoint (non-binding stop).
- Stop the study for efficacy of both the primary endpoint and secondary endpoint.
- Continue the study with initially planned sample size of 180 evaluable patients (no SSR; approximately 225 patients enrolled).
- Continue the trial and increase the sample size up to a maximum of 270 evaluable patients (approximately 338 patients enrolled).

The interim analyses will be performed by an unblinded Independent Statistical Center (ISC) and the recommendation for adaptation or early stopping will be made by the DMC. An electronic file exchange platform capable of secure storage of documents with audited access will be used to control flow of information during the study.

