9.2 SAMPLE SIZE DETERMINATION

Sample size and power was determined through simulations. The study will follow an adaptive group sequential design with unblinded sample size re-assessment. To ensure 180 evaluable patients with 7-day data and assuming a 20% dropout rate, 225 patients will be enrolled initially. An interim analysis for futility (non-binding stop) will occur after the first 60 patients complete their 7-day visit, and another interim analysis will be performed for efficacy after 120 patients for futility stopping, early efficacy stopping, and SSR (Sample Size Re-assessment). The SSR strategy will be based on both the primary endpoint and DSRS 7 days after last study treatment (key for evaluating nutritional management changes). The total sample size may be increased up to 338 patients after the second interim analysis to assure up to 270 evaluable patients.

CONFIDENTIAL Page 55 of 71

Based on prior feasibility studies (Bath et. al.²¹) the primary endpoint is hypothesized to have an odds ratio of approximately 2.2 favoring the PES group. With this effect size, the power is at least 90% for significance on the primary endpoint. Additional simulation results are provided in the Simulation Report.

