9.4 STATISTICAL ANALYSES

9.4.1 GENERAL APPROACH

Tabulations will be produced for appropriate demographic, baseline, efficacy, pharmacokinetic and safety parameters. For categorical variables, summary tabulations of the number and percentage within each category (with a category for missing data) of the parameter will be presented. For continuous variables, the mean, median, standard deviation, minimum and maximum values will be presented. Time to event data will be summarized using Kaplan-Meier methodology using 25th, 50th (median), and 75th percentiles with associated 2-sided 95% confidence intervals, as well as percent of censored observations.

Formal statistical hypothesis testing will be conducted at the 1-sided, 0.025 level of significance.

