9.4.3 ANALYSIS OF THE SECONDARY EFFICACY ENDPOINTS

The secondary efficacy endpoints will be tested for statistical significance sequentially provided the primary endpoint is found to be statistically significant. The ITT population will be used. The first endpoint tested will be FOIS at 7 days following the last investigational treatment. The second endpoint tested will be DSRS at 7 days following the last investigational treatment.

Analysis details are specified in the SAP.

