4.5. Statistical Tests and Decisions at the Interim and Final Analyses

4.5.1. Test Statistics

For the primary endpoint, independent increments of the normally distributed Wald statistic $Z = \hat{\beta}_{trt}/\widehat{SE}(\hat{\beta}_{trt})$, calculated using the GEE method with a robust sandwich estimator, are used for hypothesis testing and conditional power (CP) calculations. For the secondary endpoint, independent increments of the normally distributed Wald statistic $Z = \hat{\delta}/\widehat{SE}(\hat{\delta})$ is calculated based on estimates of treatment effect and standard error from the ANCOVA model. Conditional power is defined as the probability of reaching statistical significance at the planned final analysis (N=180) conditional on the observed effect size, assuming the current observed effect size is the true effect size.

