4.5.3. Procedure at the second interim analysis

The second interim analysis is planned for when for when 120 patients complete their 7 day visit.

Efficacy stopping: An early efficacy stopping boundary of Z > 2.5093 (one-sided P < 0.0060) will be used for all efficacy endpoints. This boundary is the group sequential boundary derived from the Lan-DeMets O'Brien Fleming spending function at 2/3 information fraction. Early stopping for efficacy will be recommended only if both the primary endpoint and secondary endpoint cross the same boundary. If the study continues, both endpoints will be tested against the group sequential boundary 1.9929 at the final analysis in a sequential manner -- the secondary endpoint is tested if the primary endpoint reaches statistical significance -- to preserve the study-wise type 1 error rate at one-sided level 0.025.

If the study is not stopped for efficacy, the interim results will be classified into different zones depending on estimation of the conditional power on the primary endpoint and, separately, on the secondary endpoint. Based on the interim zone, one of the following actions will be recommended:

- Stop the study for futility (non-binding stop).
- Continue the study until reaching the planned 180 evaluable patients (approximately 225 enrolled).
- Continue the study and increase the sample size up to a maximum of 270 evaluable patients (approximately 338 enrolled).

Details on the boundaries of these interim zones and specific actions to be taken within these zones are deferred to a restricted Simulation Report whose circulation is limited to a core study team to include the ISC and DMC in order to minimize the possibility of operational bias.

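### The efficacy stop at 120 patients rests on the primary endpoint and DSRS, but the protocol tests FOIS before DSRS, so under that order a stop can block the DSRS claim that triggered it

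*SAP*

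**What the plan says.** - **The stop rule.** SAP 4.4 gives the efficacy action at the second interim analysis as "Stop the study for efficacy of both the primary endpoint and secondary endpoint". SAP 4.5.3 states the condition: "Early stopping for efficacy will be recommended only if both the primary endpoint and secondary endpoint cross the same boundary". Both speak of a single secondary endpoint.
- **Which endpoint that is.** In SAP 4.5.1 the interim statistic for the secondary endpoint "is calculated based on estimates of treatment effect and standard error from the ANCOVA model". SAP 4.1 and 4.6.2 (the secondary analysis subsection, printed under 4.8) assign ANCOVA to DSRS and a CMH test to FOIS. SAP 4.2 also uses the singular term for DSRS and gives power for the primary plus DSRS only.
- **The boundary.** SAP 4.5.3: "An early efficacy stopping boundary of Z > 2.5093 (one-sided P < 0.0060) will be used for all efficacy endpoints". If the trial stops, FOIS therefore faces 2.5093 too, although it has no part in the decision.
- **The testing order.** Protocol 9.4.3 tests the secondaries sequentially after the primary: "The first endpoint tested will be FOIS at 7 days following the last investigational treatment". DSRS comes second. SAP 4.6.2 names only the primary as the condition for testing DSRS. SAP section 5 nevertheless reports no change from the protocol.

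**The concern.** Requiring a secondary endpoint to cross before an early stop protects the secondary claims from being judged too soon. Here it protects the endpoint that the protocol ranks second and leaves the first-ranked one out.

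The consequence depends on which document governs:

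- **Protocol 9.4.3 order (FOIS, then DSRS).** If the trial stops with FOIS at or below 2.5093, the FOIS claim fails. The sequence ends there, and the DSRS result that justified stopping cannot be claimed.
- **SAP 4.6.2 reading (DSRS after the primary only).** DSRS can be claimed. FOIS is still tested early, on about 120 patients against 2.5093, instead of on 180 against 1.9929.

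The primary claim is not at stake under either reading.

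**Working it through.** **1. Reproduce the boundary.** Inputs: one-sided 0.025 (Protocol 9.4.1, SAP 4.3.1) and a boundary "derived from the Lan-DeMets O'Brien Fleming spending function at 2/3 information fraction" (SAP 4.5.3).

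Alpha spent = 2[1 - Φ(z(0.9875)/√(2/3))] = 2[1 - Φ(2.2414/0.8165)] = 0.00605, so Z = 2.5093. With correlation √(2/3) between looks, the final boundary is 1.9929. Both match SAP 4.5.3. (SAP 4.5.4 prints 2.5093 as the final critical value. That is a separate inconsistency; 1.9929 is used here.)

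**2. Effects on the Z scale.** Allocation is taken as 1:1.

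- DSRS (SAP 4.2: difference 1.75, SD 4). At 180: 1.75/(4√(2/90)) = 2.93. At 120: 1.75/(4√(2/60)) = 2.40.
- P(DSRS > 2.5093 at 120) = 1 - Φ(2.5093 - 2.3963) = 0.455.
- P(DSRS > 1.9929 at 180) = 1 - Φ(1.9929 - 2.9348) = 0.827.
- Primary: SAP 4.2 states 95% power. A drift of 3.62 at full information gives 95% with the two boundaries and no sample size re-assessment. At 120 it is 3.62 × √(2/3) = 2.96, and P(cross) = 0.674.

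**3. Probability of a stop.** P(primary and DSRS both > 2.5093) is 0.31-0.41 for a correlation between them of 0 to 0.7, and about 0.35 at 0.3.

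**4. FOIS at a stop.** The documents give neither a FOIS effect nor any correlations. Assumed: correlation of the primary with each secondary 0.3; FOIS-DSRS correlation 0.6 to 0.9; FOIS drift 1, 0.85 or 0.5 times that of DSRS; no sample size re-assessment. Trivariate normal increments were simulated at the two looks.

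| FOIS effect relative to DSRS | FOIS ≤ 2.5093, given a stop | Stop with FOIS short, all trials | P(stop) if FOIS must also cross |
|---|---|---|---|
| Equal | 14-29% | 5-10% | 25-30% |
| 15% smaller | 32-45% | 11-16% | 19-24% |
| Half | 77-80% | 27-28% | 7-8% |

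The third column is the second multiplied by 0.35, for example 0.29 × 0.35 = 0.10 and 0.45 × 0.35 = 0.16.

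**5. What an early stop gives up.** At an equal effect, FOIS alone has a 46% chance of crossing at 120 and an 83% chance at 180 (step 2). Among stops with FOIS short, FOIS and the primary would both have passed 1.9929 at 180 in 71-91% of cases across the first two settings.

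| FOIS effect relative to DSRS | All three endpoints won, current rule | All three won if FOIS must also cross |
|---|---|---|
| Equal | 63-71% | 71-76% |
| 15% smaller | 51-57% | 62-66% |

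**6. Type 1 error if FOIS is added to the stop.** For each endpoint, rejection still requires Z > 2.5093 at a stop or Z* > 1.9929 at the end. The union of those two events has null probability 0.025 whatever the stopping condition, so a stricter stop cannot raise the error above 0.025.

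**The case against.** **DSRS as the stopping endpoint is a legible choice.** Protocol 9.2 says: "The SSR strategy will be based on both the primary endpoint and DSRS 7 days after last study treatment", and calls DSRS key for nutritional management. That sentence concerns the re-assessment, not the efficacy stop, but SAP 4.2 also powers the trial for the primary plus DSRS and gives nothing for FOIS. The stop protects what the trial was sized for. This stands, and it is why ranking DSRS first is a legitimate repair. It does not explain why the protocol ranks FOIS first.

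**The DSRS block depends on the testing order.** A reader might infer that the flaw remains whatever order is adopted. The documents do not support that: under SAP 4.6.2 DSRS needs only the primary, and putting DSRS first removes the block. Only the early test of FOIS survives any order. Protocol 9.4.3 also does not say outright that a failed FOIS ends testing; that is the natural meaning of sequential testing, not an explicit rule.

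**A stop is not automatic, nor does it wholly freeze FOIS.** SAP 4.5.3 sets a necessary condition, and the DMC may decline to recommend stopping. Protocol 7.3 keeps collecting follow-up on patients already enrolled. Both points stand, but the SAP gives no rule for weighing FOIS at that meeting or for testing data that arrive after a stop.

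**The frequencies are conditional on assumptions.** They rest on a FOIS effect and correlations that the documents do not give, and they omit the increase to 270, whose zones are in the restricted Simulation Report. This stands. The mismatch in the text does not depend on them.

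**Conclusion.** The stop rule and the protocol's testing order do not fit together, and the two documents disagree on that order. Under Protocol 9.4.3, an efficacy stop can forfeit both secondary claims, including the one that triggered it. Under SAP 4.6.2, it can forfeit FOIS only.

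Under the stated assumptions, about 35% of trials stop at 120. A stop with FOIS short occurs in about 5-10% of all trials at an equal FOIS effect, 11-16% at one 15% smaller and 27-28% at half. The percentages conditional on a stop are larger and should not be read as the chance that the trial meets this problem. The primary claim and the overall type 1 error are unaffected. The point should be settled before the second interim analysis.

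**What to change.** State one secondary testing order in Protocol 9.4.3 and SAP 4.6.2, and make SAP 4.4 and 4.5.3 name the endpoints that the stop depends on. Either route works:

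- **(a) Rank DSRS ahead of FOIS in both documents.** The stop rule and its probability stay as they are, and the endpoint that triggers a stop can be claimed. The cost is accepting openly that FOIS may be tested early against 2.5093.
- **(b) Keep FOIS first and add it to the stop.** Suggested text: *An efficacy stop is recommended only when the primary endpoint, FOIS at 7 days and DSRS at 7 days each exceed 2.5093; if any does not, the study continues.* Define the stage-1 FOIS statistic as the signed square root of the CMH statistic. The cost is fewer early stops: from about 35% to 25-30% (equal effect), 19-24% (15% smaller) or 7-8% (half). The simulations behind SAP 4.2 must be rerun, and the independent statistical center reports one more statistic. Type 1 error does not rise.

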4.5. Statistical Tests and Decisions at the Interim and Final Analyses

4.5.1. Test Statistics

For the primary endpoint, independent increments of the normally distributed Wald statistic $Z = \hat{\beta}_{trt}/\widehat{SE}(\hat{\beta}_{trt})$, calculated using the GEE method with a robust sandwich estimator, are used for hypothesis testing and conditional power (CP) calculations. For the secondary endpoint, independent increments of the normally distributed Wald statistic $Z = \hat{\delta}/\widehat{SE}(\hat{\delta})$ is calculated based on estimates of treatment effect and standard error from the ANCOVA model. Conditional power is defined as the probability of reaching statistical significance at the planned final analysis (N=180) conditional on the observed effect size, assuming the current observed effect size is the true effect size.

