4.5.4. Procedure at the final analysis

At the time of the final analysis, hypothesis testing for the primary and secondary endpoints will be performed using a weighted combination statistic (Lehmacher and Wassmer 1999; Cui et al. 1999), whereby the Z-statistic from the first stage of the study (the first 120 patients, i.e., 2/3 of the planned information), Z_1 , is combined with the independent Z-statistic from the remaining patients, Z_2 , using prespecified weights $w_1 = \sqrt{0.67}$ and $w_2 = \sqrt{0.33}$ to form a combination statistic $Z^* = w_1 Z_1 + w_2 Z_2$. These weights are used regardless of whether the sample size is increased beyond 180. If $Z^* > 2.5093$, statistical significance is achieved for that endpoint.

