4.5.5. Type 1 Error Control

To see that Type 1 error is theoretically controlled even though sample size may be modified in a data-dependent manner, note that under the null hypothesis for the primary endpoint, the incremental statistics for the 2 stages, are independent with asymptotic N(0,1) distribution, regardless of final sample size.

Therefore the final test statistic is normal with mean 0 and variance $w_1^2 + w_2^2 = 1$. It follows that the joint distribution of $w_1Z_1 + w_2Z_2$ is the same as for the standard group sequential test with correlation w_1 at interim, as shown by Cui, Hung and Wang (1999). Because the pre-specified fixed weights w_1 and w_2 are used regardless of whether the sample size is modified based on interim data, the combination statistic with standard group sequential efficacy boundaries properly controls type 1 error. The same principles apply to the secondary endpoint.

Results of simulations performed under various null scenarios confirming type 1 error control are summarized in the Simulation Report.

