4.6.2 Secondary Efficacy Analysis

The secondary endpoints are FIOS and DSRS 7 days (+/- 1 day) after completion of investigational treatment.

The ordered categorical endpoint of FIOS will be analyzed by a Cochran-Mantel-Haenszel (CMH) test stratified by site and baseline PAS, using the modified ridit score and test of "row mean scores different" to take into account the ordered nature of the response.

The secondary endpoint of DSRS will be modeled by an ANCOVA model with treatment, center, baseline PAS and baseline DSRS as predictors, and will be tested for statistical significance provided the primary endpoint is found to be statistically significant. The ITT population will be used.

Missing data on the secondary endpoint will not be imputed for the purpose of significance testing.

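### Stage-wise Wald statistics from about 120 and 60 patients are referred to normal boundaries without a small-sample reference, which can lift the one-sided type 1 error slightly above 0.025 (to about 0.027 for DSRS)

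*SAP*

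**What the plan says.** SAP 4.3.1 sets "all tests conducted at the 1-sided, 0.025 level of significance". SAP 4.5.3 states: "An early efficacy stopping boundary of Z > 2.5093 (one-sided P < 0.0060) will be used for all efficacy endpoints". That boundary is "derived from the Lan-DeMets O'Brien Fleming spending function at 2/3 information fraction". If the trial continues, "both endpoints will be tested against the group sequential boundary 1.9929 at the final analysis". Stopping early for efficacy requires the primary and the secondary endpoint both to cross at the second interim analysis, and the secondary is tested at the end only if the primary is significant.

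The primary statistic is a Wald Z "calculated using the GEE method with a robust sandwich estimator, are used for hypothesis testing and conditional power (CP) calculations" (SAP 4.5.1). DSRS "will be modeled by an ANCOVA model with treatment, center, baseline PAS and baseline DSRS as predictors" (SAP 4.6.2), and SAP 4.5.1 takes its estimate/SE as normal. In SAP 4.5.4 the statistic from the first 120 patients "is combined with the independent Z-statistic from the remaining patients", with weights √0.67 and √0.33. SAP 4.5.5 argues that under the null "the incremental statistics for the 2 stages, are independent with asymptotic N(0,1) distribution, regardless of final sample size". It then refers to null simulations in a separate Simulation Report, which is said to confirm error control.

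SAP 4.5.4 prints 2.5093 as the final critical value, in conflict with the 1.9929 of SAP 4.5.3.

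**The concern.** The combination test keeps its level if each stage statistic is standard normal under the null. An ANCOVA estimate divided by its estimated standard error is a t statistic, and its tails are heavier than normal. An uncorrected sandwich standard error tends to be too small when there are few clusters, and here the patients are the clusters: about 120 in stage 1 and 60 in stage 2. Fitting the stages separately makes this worse than one fit to 180 patients would, because stage 2 pays for its own intercept, covariates and center terms out of about 60 patients.

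At stake is the stated 0.025 level in a trial meant to support a de novo submission. The effect can only be small, but it pushes the error upward.

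**Working it through.** **1. The SAP's boundaries.** Spending 2[1 − Φ(z₀.₉₈₇₅/√t)] at t = 2/3 gives 0.00605, so the interim boundary is 2.5093. With 1.9929 at the end, P(Z₁ > 2.5093 or Z* > 1.9929) under exact normality is 0.02500, or 0.02498 with the rounded weights 0.67 and 0.33. The plan's figures reproduce.

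**2. Residual degrees of freedom for DSRS.** The documents give none. With all 15 centers present in both stages, the ANCOVA has 1 intercept + 1 treatment + 14 center + 1 baseline PAS + 1 baseline DSRS = 18 parameters. That leaves 120 − 18 = 102 and 60 − 18 = 42. At the other extreme, intercept and treatment only leave 118 and 58.

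**3. DSRS alone, rejecting if either look crosses.** Replace the normals by independent t variables and integrate P(T₁ > 2.5093) + P(T₁ ≤ 2.5093, √0.67·T₁ + √0.33·T₂ > 1.9929):

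| Residual df (stage 1 / stage 2) | Interim | Overall |
|---|---|---|
| Normal | 0.0060 | 0.0250 |
| 118 / 58 | 0.0067 | 0.0266 |
| 102 / 42 | 0.0068 | 0.0270 |
| 102 / 132 (stage 2 of 150 patients) | 0.0068 | 0.0263 |

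Stages of 150 and 75 patients give 0.0265 overall.

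**4. The SAP's actual rule.** Early rejection counts only if both endpoints exceed 2.5093. This was simulated with 4 million draws per setting and between-endpoint correlations from 0 to 0.7. At the planned DSRS effect the interim mean of the DSRS statistic is 1.75 / (4·√(4/120)) = 2.40.

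- Primary null, exact normality: 0.0232-0.0250.
- Primary null, t statistics (used as a stand-in for small-sample behavior), DSRS also null: 0.0246-0.0252.
- The same with DSRS at its planned effect (difference 1.75, SD 4): 0.0256-0.0270.
- DSRS null, primary at its planned 95% power, DSRS tested only after the primary, 102/42 df: about 0.025 at zero correlation, about 0.027 at correlations of 0.3-0.5.

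**5. Primary GEE, rejecting if either look crosses.** Null trials were generated with 12 boli per patient and an assumed patient random effect. They were analyzed with the SAP's cumulative logit model, independence working correlation and uncorrected sandwich. With 40,000 trials per scenario and random-effect SD 2 or 3, the error was 0.0272-0.0278 at 120/60 (simulation SE 0.0008) and 0.0255-0.0264 at 120/150. A separate run of 12,000 trials gave 0.0254-0.0256 at 120/60 (SE about 0.001). Another run, at SD 2.5, gave 0.0284-0.0287 (SE 0.0007), but the runs at SD 2 and 3 on either side of it did not exceed 0.0278. About 0.025-0.028 is a fair summary. A Mancl-DeRouen-type correction brought the simulated error to 0.023-0.025.

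**6. If the final boundary were 2.5093.** The overall error would be about 0.007-0.0115, well below 0.025.

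**The case against.** The strongest reply is that SAP 4.5.5 does not rest on asymptotics alone. It cites null simulations that are said to confirm error control. The report is not among the documents, so a reader who inferred that the finite-sample question was overlooked would be going beyond them. What stands is that the SAP does not say whether those simulations used the uncorrected sandwich and the center-adjusted ANCOVA at stage sizes 120/60.

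Second, requiring both endpoints to cross discards interim crossings by one endpoint alone, and this offsets most or all of the excess when the other endpoint has no effect. Testing DSRS only after the primary also lowers its error, and the protocol's placing of FOIS before DSRS (section 9.4.3) could only lower it further. These are real offsets, but they weaken as the other endpoint's effect grows, and the level has to hold whatever that effect is.

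Third, the stages may be larger. The primary is analyzed on the ITT population with multiple imputation, so 225 enrolled could mean stages nearer 150 and 75, and stage 2 can grow to 150 evaluable patients. The excess then shrinks, though for DSRS it does not vanish. DSRS is not imputed, so 120/60 remains the natural case for it.

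Fourth, uncorrected sandwich Wald tests with 60-120 clusters are common practice. That is fair, and it is one reason to rate the point as minor.

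**Conclusion.** The point holds as a minor one. For DSRS taken alone, with rejection at either look, the error is about 0.0265-0.0270 instead of 0.025, and about 0.0067-0.0068 instead of 0.0060 at the interim, assuming 42-58 residual degrees of freedom in stage 2. Under the SAP's full rule it lies between about 0.025 and 0.027. For the primary it is about 0.025-0.028 at 120/60.

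A reader might infer that the true error is a fixed value as high as 0.029, or that the 0.025 claim simply fails. The documents support neither. No run reached 0.029, and some scenarios give 0.025. The primary figure depends on an assumed within-patient correlation and assumed category proportions, and the simulations leave out imputation, site effects and minimization.

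All these figures presume that the final boundary is settled at 1.9929, the value that gives a total of 0.025 with 2.5093 at the interim. That conflict between SAP 4.5.3 and 4.5.4 moves the error rate far more than this point does and must be resolved first.

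**What to change.** In SAP 4.5.1 and 4.5.4, define each stage statistic as Z_k = Φ⁻¹(1 − p_k), where p_k is the one-sided stage p-value. This is the inverse-normal form of the Lehmacher-Wassmer method that the SAP already cites. For DSRS, take p_k from the t distribution with the residual degrees of freedom of that stage's ANCOVA.

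For the primary, either name a small-sample-corrected sandwich estimator (Mancl-DeRouen or Morel-Bokossa-Neerchal), or state in SAP 4.5.5 that the Simulation Report's null runs used the uncorrected sandwich at stage sizes 120/60 and held 0.025. If a correction is adopted, re-run the null simulations with it. Use the same statistics for conditional power.

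The cost is SAP wording and minor programming; no design change or new data are needed. Power falls by under 1 point: if the critical values are in effect 2.5-3% larger, the stated 95% for the primary becomes about 94.3-94.5%.
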